14. ETHICAL AND REGULATORY CONSIDERATIONS

14.1. Declaration of Helsinki

The Chief Investigator will ensure that this study is conducted in accordance with the principles of the Declaration of Helsinki.

14.2. ICH Guidelines for Good Clinical Practice

The Chief Investigator will ensure that this study is conducted in accordance with relevant regulations and Good Clinical Practice.

14.3. Approvals

The protocol, informed consent form, participant information sheet and any other patient or consultee documents will be approved by the Sponsor before being submitted to an appropriate Research Ethics Committee (REC) for written approval. No study procedures will take place before the REC has given a favourable opinion. The Chief Investigator will obtain written approval from the Sponsor and the REC for any substantial amendment to the original-approved documents before any changes are implemented.

14.4. Reporting

Throughout the study, the Chief Investigator will submit an Annual Progress Report to the REC and the Sponsor once a year, or more frequently on request. In addition, an End of Study Notification and Final Report will also be submitted to the REC and Sponsor within the required timelines. Any additional reports required will be submitted upon request (e.g. Trust R&D, funder).

14.5. Participant Confidentiality

The study team will ensure that each participant's participation is maintained confidential at all times. All documents and databases will be stored securely and will be accessible to study staff and authorised personnel only. The study will comply with the Data Protection Act, which requires data to be anonymised as soon as is practical. The participants will be identified by initials, NHS number and study number only on the electronic CRF. Encrypted administrative databases, maintained separately from the electronic CRFs, will contain each participant's contact details for the purposes of follow-up at each recruiting site. Access to the administrative databases will be restricted to the study teams. The electronic CRFs will be managed by the CTU. All databases will be archived for 5 years following completion of the study.

Inclusion of the NHS number reflects a requirement for the primary identifier to take a single alphanumeric format on the electronic database for randomisation, prevention of duplication and to allow for mortality checks prior to attempting to contact participants for follow up data. In the event that a participant has passed away, follow up data will be obtained through the GP by the local study team.

14.6. Expenses and Benefits

There will be no expenses or other payments to participants in this study. No visits additional to normal care are required so no expenses will be incurred. There are no know benefits for patients in either group but both groups will help to inform NHS practice in relation the risk of post-operative infection.

14.7. Other Ethical Considerations

The interventions (either FAW or RFW) in this trial are minimally invasive. Both technologies are licenced, equally effective at preventing inadvertent perioperative hypothermia and are in routine use in the NHS. There is no evidence to suggest that either method should be used preferentially for any individual or group of patients. Currently, the choice of warming method is governed by local availability or personal preference of the anaesthetic or surgical team involved. Outside the context of a trial, patients are generally unaware that active warming during surgery forms part of their care. As a consequence, and in

the absence of any trial specific clinic visits or clinical investigations, the consenting process is weighted on follow-up data (including access to healthcare records) and questionnaires.

Due to the inevitable history of trauma, high incidence of comorbidities and urgent nature of surgery, we believe it inappropriate routinely ask potential participants to review, weigh up and retain information relating to the trial preoperatively. We are likely therefore to seek consultee agreement in a significant number of participants. We feel this is justified on grounds that participants' optimal medical and surgical management, including psychological care, should not be delayed or jeopardised in relation to the trial. Precedent for this model of consent specifically in this patient group comes from the WHiTE cohort and associated randomised controlled trials (Griffin et al., 2013; Sims et al., 2016).

Of the three initial pilot sites, one currently uses FAW exclusively, one uses RFW exclusively and the third uses a combination of FAW and RFW according to preference of the anaesthetic and surgical teams. The investigators from all three sites have expressed equipoise in relation to the choice of warming technology and their associated efficacy and clinical outcomes.

15. FINANCE AND INSURANCE

15.1. Funding

This study is funded by the Healthcare Infection Society and by the company 3MTM (Patient Warming Solutions).

15.2. Insurance

NHS Indemnity will apply.

18. APPENDIX A: PARTICIPANT FOLLOW-UP TELEPHONE EQ-5D-5L QUESTIONNAIRE

^[Site to insert details] RIIO Pilot Study Participant Follow-Up Telephone EQ-5D-5L Questionnaire				
Study Number:	Date of Completion:			
Follow-up Time Point: 30 (+/- 7) days (Tick ONE)	90 (+/- 14) days			
SECTION 1 All of the questions in this section relate to the participant's health on the day that the questionnaire is completed				
Mobility I have no problems in walking about I have slight problems in walking about I have moderate problems walking about I have severe problems walking about I am unable to walk about	Pain/Discomfort I have no pain or discomfort I have slight pain or discomfort I have moderate pain or discomfort I have severe pain or discomfort I have extreme pain or discomfort			
Anxiety/Depression I am not anxious or depressed	Self-Care I have no problems with caring for myself			

I am slightly anxious or depressed

I am moderately anxious or depressed

I am severely anxious or depressed

I am extremely anxious or depressed

/		
	Self-Care	_)
	I have no problems with caring for myself	
	I have slight problems washing or dressing myself	
	I have moderate problems washing or dressing myself	
	I have severe problems washing or dressing myself	\square
	I am unable to wash or dress myself	\cup

RIIIO Pilot Study Participant Follow-Up EQ-5D-5L Questionnaire v2.0 (20th January 2017)

[Site to insert details]

RIIiO Pilot Study

Usual Activities (e.g. work, study, housework, family or leisure activities)

I have no problems with performing my usual activities

I have slight problems with performing my usual activities

I have moderate problems with performing my usual activities

I have severe problems with performing my usual activities

I am unable to perform my usual activities

Health State

Well-being score **TODAY** on a scale of 0-100, where 100 is the best possible health state and zero is the worst possible health state

SECTION 2

Read out the questions below. Record the participant's answers and any further comments they make

Surgical Wound		
Have you had any concerns about the wound from your hip operation since you were last contacted by the RIIiO Study Team?	Yes	No 🗌
Participant's Comments:		

RIIO Pilot Study Participant Follow-Up EQ-5D-5L Questionnaire v2.0 (20th January 2017)

[Site to insert details]

RIIiO Pilot Study

Further Surgery)
Have you had any further surgery on your affected hip since you were last contacted by the $R//iO$ Study Team?	
If yes, what was the date(s) of the surgery?	
Details of the operation:	
Participant's Comments:	
	/

Form Completed by:

Print Name

Signature

RIIIO Pilot Study Participant Follow-Up EQ-5D-5L Questionnaire v2.0 (20th January 2017)

		-	-		
Cito :	6 m.	incode	da	ما أنصا	- 1
[Site :	ю.	ILISHI	OB	24112	61

RIIiO Pilot Study

Prescription(s)		
Have you taken antibiotics for your wound since you were last contacted by the RHiO Study Team?	Yes	No
If yes, what was the date(s) of the prescription(s)?		
Participant's Comments:		
Readmission(s)		
Have you been readmitted to any hospital since you were last contacted by the $RHiO$ Study Team?	Yes	No
If yes, what was the date(s) of admission(s)?		
Participant's Comments:		

RIIIO Pilot Study Participant Follow-Up EQ-5D-5L Questionnaire v2.0 (20th January 2017)

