7.6. Subsequent Assessments

The participant will be contacted for follow-up at the following time points after surgery:

- 1) 30 (+/- 7) days
- 2) 90 (+/- 14) days

Follow-up assessments will be undertaken by a member of the local study team through a) medical records and b) direct contact, usually by telephone, with the participant or their consultee. The participant will not be asked to attend any research specific clinic visits and they will not be visited at home by the study team. If it is not possible to make contact with the participant, the local study team will gather follow-up data from the patient's GP and from routinely collected surveillance data. At each time point, we will ask questions about the participant's wellbeing, surgical scar and any treatment or concerns around possible infection at the operative site. Where necessary, further clinical review will be requested.

The study will use the participant follow-up telephone questionnaire in Appendix A as a research tool when gathering patient reported outcome measures for quality of life (PROMS) and any relevant concerns they have. Instructions to the participant will be dictated from the EQ-5D-5L telephone questionnaire in Appendix B. If a patient lacks capacity, the EQ-5D-5L Proxy version 1 will be used (Appendix C).

Deep SSI will be defined by the following criteria:

- a. Infection arising within 90 days of the index surgery (where day 1 is the procedure date) AND
- b. Involves deep tissues related to the incision (e.g. fascial and muscle layers, joint space or periprosthetic region)

AND

- c. At least one of the following
 - i. Purulent drainage from the deep incision or periprosthetic drain.
 - ii. A deep incision that spontaneously dehisces, or is deliberately opened or aspirated or biopsied by a surgeon, physician or other designee and an organism is identified by a culture or non-culture based microbiologic testing method which is performed for purposes of clinical diagnosis or treatment (e.g., not Active Surveillance Culture/Testing) or culture or non-culture based microbiologic testing method is not performed
 - An abscess or other evidence of infection involving the deep incision or periprosthetic region that is detected on gross anatomical, histopathological exam or imaging test

Superficial SSI will be defined by the following criteria:

- a. Infection arising within 30 days of the index surgery (where day 1 is the procedure date) AND

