11. ECONOMIC EVALUATION

Good practice recommendations for cost-effectiveness analyses (Ramsey et al, 2015) suggest concentrating on the measurement of large cost drivers, with less focus on resources that are not expected to differ between different treatments. Estimation of cost-effectiveness is therefore an iterative process and, by including a health economic component, it is possible to consider how the methods might be refined in any future more definitive study.

Methods

In order to estimate costs, we will measure theatre time, length of stay and hospital re-admissions. Unit costs (e.g. Curtis et al, 2015, Dept of Health, 2014-2015) will subsequently be assigned to items of resource use. However, in order to estimate the unit costs associated with both the RAW and FAW intervention, each site will be asked to complete a short questionnaire which would request information such as the purchase price of intervention specific equipment and whether items are disposed of after each patient or re-used.

For benefits, the EQ-5D-5L (Herdman et al, 2011) will be used to measure quality of life, enabling QALY (Quality Adjusted Life Year) scores to be calculated. This will be requested at baseline, day 30 and day 90. The self-complete version of the EQ-5D-5L will be used for those who give consent, consultees will be asked to complete the proxy version of the EQ-5D-5L.

Analysis

The main purpose of the analysis is to inform the decision regarding how and what cost and effect data would be collected within the proposed fully powered trial. Thus, we will estimate completion rates and seek to identify big cost drivers, in order to inform this decision.

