19. APPENDIX B: EQ-5D-5L TELEPHONE QUESTIONNAIRE

Health Questionnaire

English version for the UK

SCRIPT FOR TELEPHONE INTERVIEW

GENERAL INTRODUCTION

It is suggested that the telephone interviewer follows the script of the EQ-5D. Although allowance should be made for the interviewer's particular style of speaking, the wording of the questionnaire instructions should be followed as closely as possible. In the case of the EQ-5D descriptive system on pages 2 and 3, the precise wording must be followed.

It is recommended that the interviewer has a copy of the EQ-5D in front of him or her as it is administered over the telephone. This enables the respondent's answers to be entered directly on the EQ-5D by the interviewer on behalf of the respondent (i.e. the appropriate boxes on pages 2 and 3 are marked and the scale on page 4 is marked at the point indicating the respondent's 'health today'). The respondent should also have a copy of the EQ-5D in front of him or her for reference. If the respondent asks for clarification, the interviewer can help by rereading the question verbatim. The interviewer should not try to offer his or her own explanation but suggest that the respondent uses his or her own interpretation.

If the respondent has difficulty regarding which box to mark, the interviewer should repeat the question verbatim and ask the respondent to answer in a way that most closely resembles his or her thoughts about his or her health today.

INTRODUCTION TO EQ-5D

(Note to interviewer: please read the following to the respondent)

We are trying to find out what you think about your health. I will first ask you some simple questions about your health TODAY. I will then ask you to rate your health on a measuring scale. I will explain what to do as I go along but please interrupt me if you do not understand something or if things are not clear to you. Please also remember that there are no right or wrong answers. We are interested here only in your personal view.

EQ-5D DESCRIPTIVE SYSTEM: INTRODUCTION

First I am going to read out some questions. Each question has a choice of five answers. Please tell me which answer best describes your health TODAY. Do not choose more than one answer in each group of questions.

(Note to interviewer: it may be necessary to remind the respondent regularly that the timeframe is TODAY. It may also be necessary to repeat the questions verbatim)

EQ-5D DESCRIPTIVE SYSTEM

MOBILITY

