First I'd like to ask you about mobility. Would you say that:

- 1. You have no problems in walking about?
- 2. You have slight problems in walking about?
- 3. You have moderate problems in walking about?
- 4. You have severe problems in walking about?
- 5. You are unable to walk about?

(Note to interviewer: mark the appropriate box on the EQ-5D questionnaire)

SELF-CARE

Next I'd like to ask you about self-care. Would you say that:

- 1. You have no problems washing or dressing yourself?
- 2. You have slight problems washing or dressing yourself?
- 3. You have moderate problems washing or dressing yourself?
- 4. You have severe problems washing or dressing yourself?
- 5. You are unable to wash or dress yourself?

(Note to interviewer: mark the appropriate box on the EQ-5D questionnaire)

USUAL ACTIVITIES

Next I'd like to ask you about usual activities, for example work, study, housework, family or leisure activities. Would you say that:

- 1. You have no problems doing your usual activities?
- 2. You have slight problems doing your usual activities?
- 3. You have moderate problems doing your usual activities?
- 4. You have severe problems doing your usual activities?
- 5. You are unable to do your usual activities?

(Note to interviewer: mark the appropriate box on the EQ-5D questionnaire)

PAIN / DISCOMFORT

Next I'd like to ask you about pain or discomfort. Would you say that:

- 1. You have no pain or discomfort?
- 2. You have slight pain or discomfort?
- 3. You have moderate pain or discomfort?
- 4. You have severe pain or discomfort?
- 5. You have extreme pain or discomfort?

(Note to interviewer: mark the appropriate box on the EQ-5D questionnaire)

ANXIETY / DEPRESSION

Finally I'd like to ask you about anxiety or depression. Would you say that:

- 1. You are not anxious or depressed?
- 2. You are slightly anxious or depressed?
- 3. You are moderately anxious or depressed?
- 4. You are severely anxious or depressed?
- 5. You are extremely anxious or depressed?

(Note to interviewer: mark the appropriate box on the EQ-5D questionnaire)

The best health you can imagine

EQ VAS: INTRODUCTION

(Note to interviewer: if possible, it might be useful to send a visual aid (i.e. the EQ VAS) before the telephone call so that the respondent can have this in front of him or her when completing the task)

Now, I would like to ask you to say how good or bad your health is TODAY.

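### The Appendix A follow-up form departs from the EQ-5D-5L wording that Appendix B requires, and section 11 names a different mode of collection from section 7.6 at days 30 and 90

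*Protocol*

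**What the plan says.** Four places in the protocol govern how the EQ-5D-5L is collected.

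- **Section 7.6 (Subsequent Assessments).** Follow-up at days 30 and 90 uses medical records and "direct contact, usually by telephone, with the participant or their consultee". On quality of life it states: "The study will use the participant follow-up telephone questionnaire in Appendix A as a research tool". Appendix B is given a narrower role, as the source of the instructions dictated to the participant.
- **Appendix A.** The form (version 2.0, 20 January 2017) has tick boxes for the day 30 and day 90 contacts. Its self-care item opens with "I have no problems with caring for myself".
- **Appendix B.** The telephone script words the same level as "You have no problems washing or dressing yourself". It allows interviewers some latitude of style elsewhere, but for the descriptive system "the precise wording must be followed".
- **Section 11 (Economic Evaluation).** The instrument is timed as follows: "This will be requested at baseline, day 30 and day 90". On the version to be used: "The self-complete version of the EQ-5D-5L will be used for those who give consent, consultees will be asked to complete the proxy version". QALYs are to be calculated from these responses.

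**The concern.** The EQ-5D-5L is scored on the premise that respondents chose among fixed descriptions. The form named as the research tool alters some of those descriptions, against the protocol's own wording rule, and one alteration changes what is being asked. Two sections also describe the mode of collection differently for the same follow-up contacts.

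The pilot's secondary objective is to test the collection of quality-of-life and resource data and to confirm the health-economic method for the full trial. Section 3 adds that pilot data will pass into the full trial's final analysis. Non-standard items on the follow-up form could therefore be carried forward, and the utilities might not be comparable with those from standard administrations, with baseline, or between sites that use the two appendices differently.

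**Working it through.** The protocol gives no figure to reproduce on this point. The check is a comparison of texts.

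**Step 1: response options.** The descriptive system has 5 dimensions with 5 levels each, 5 × 5 = 25 options. Each Appendix B option was turned from the second person to the first and compared with Appendix A.

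| Dimension | Levels that differ | Nature of the difference |
|---|---|---|
| Mobility | 3, 4 | the preposition *in* is dropped |
| Self-care | 1 | *caring for* replaces *washing or dressing* |
| Usual activities | 1 to 5 | *performing* or *perform* replaces *doing* or *do* |
| Pain/discomfort | none | – |
| Anxiety/depression | none | – |

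Total: 2 + 1 + 5 + 0 + 0 = 8 of 25 differ, and 25 − 8 = 17 match. Of the 8, only self-care level 1 changes content; the other 7 leave the meaning essentially intact.

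**Step 2: the self-care item within Appendix A.** Level 1 refers to caring for oneself in general, while levels 2 to 5 return to washing or dressing. Take a participant who washes and dresses without difficulty but has some other difficulty in caring for themselves. Under Appendix B, level 1 is the accurate answer. Under Appendix A, level 1 is not strictly true and neither is any of levels 2 to 5. The item is thus inconsistent with itself as well as with the script. The line appears twice in the text with the same wording, so it does not look like an extraction fault.

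**Step 3: the visual analogue scale.** Appendix A calls it a well-being score and anchors it at the best and worst *possible* state. Appendix B asks about health and anchors the scale at the best and worst the respondent can *imagine*. Label and anchors both differ.

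**Step 4: which text participants hear.** Section 7.6 names Appendix A as the questionnaire and gives only the instructions to Appendix B. Read literally, the items come from Appendix A. The internal layout of the two appendices suggests otherwise (see the objection). The protocol does not resolve it, and sites could reasonably do either.

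**Step 5: mode.**

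| | Section 7.6 | Section 11 |
|---|---|---|
| Time points | days 30 and 90 | baseline, days 30 and 90 |
| Participant able to respond | telephone form, usually by telephone | self-complete version |

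Because section 11 covers all three time points, its self-complete statement cannot be confined to baseline. Taken at face value, the two sections name different modes at days 30 and 90.

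**The case against.** The strongest reply is that Appendix A is only a recording sheet. Its Section 1 carries no instruction to read the items aloud, whereas its Section 2 does. Its items are in the first person, while Appendix B uses the spoken second person. After each dimension Appendix B tells the interviewer to mark a box on a questionnaire, and Appendix A is the only participant follow-up form shown. Appendix B also contains every item and the scale task, which would be needless if it supplied only an introduction. On this reading participants hear the standard wording.

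That reply stands as far as it goes. A reader might infer that the pilot's quality-of-life data are definitely not from a standard instrument, and the document does not support that. The reply does not cure the form, however: section 7.6 does not say that items are read from Appendix B, and an interviewer who reads the standard self-care level 1 must still tick a box that says something else.

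On mode, *self-complete* in section 11 is contrasted only with *proxy*, so it may have been meant as self-report in general. That is plausible and makes the repair small, but it is not what the term ordinarily conveys.

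Three further inferences are tempting and should not be drawn:

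- **That the sections conflict on when a proxy answers.** Section 7.6 goes by capacity and section 11 by consent, but section 7.3 largely aligns the two. Participants are asked for their own consent after surgery, and a consultee's written agreement is sought where incapacity persists.
- **That utilities shift in a known direction or by a known amount.** Someone with other care difficulties finds no better fit below level 1 and may stay there. The document gives no response distribution and no value set.
- **That completion rates cannot be attributed to a mode.** That would require knowing that the electronic CRF omits mode, and the protocol does not show the CRF.

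**Conclusion.** The point holds in a limited form. Appendix A breaks the protocol's own rule on wording: 8 of 25 options differ from Appendix B, 1 of them in content, and the scale's label and anchors differ too. Non-standard wording is certain for the form and possible for what participants hear. Section 11 also needs to be reconciled with section 7.6 on mode at days 30 and 90.

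The size of any effect on utilities cannot be calculated from the document. What is exposed is the level of the utilities and their comparability over time, between sites and with other data. Both arms use the same form and are followed up in the same way, so no bias in the between-arm comparison is shown. This is a secondary endpoint of a pilot, and the impact is modest. It is still worth correcting, because these responses feed the QALYs and the pilot data are intended for the full trial.

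**What to change.** 1. Replace the five Appendix A items and the visual analogue scale with the Appendix B wording, adapted only for grammatical person.
2. State in section 7.6 that the items, and not only the instructions, are read from Appendix B and that Appendix A records the answers.
3. Amend section 11 to telephone administration at days 30 and 90, in line with section 7.6, and state the baseline mode separately.
4. Flag EQ-5D-5L responses already collected on version 2.0 of Appendix A, so that the health-economic analysis and any transfer to the full trial can distinguish them.

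The cost is one form revision, wording edits in two sections and a version flag in the data set. Participants face no added burden, and neither the sample size nor the main analysis changes. The one drawback is that two form versions will exist within the pilot, which the flag handles.
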